10.3.4 Additional Events Reported

Additional events that require reporting

In addition to the above criteria, AEs meeting either of the below criteria, although not serious per ICH definition, are reportable to the Sponsor.

- Is a cancer
- Is associated with an overdose

10.3.5 Recording AE and SAE

AE and SAE recording

- When an AE/SAE occurs, it is the responsibility of the investigator to review all documentation (eg, hospital progress notes, laboratory, and diagnostics reports) related to the event.
- The investigator will record all relevant AE/SAE information on the AE CRFs/worksheets at each examination.
- It is not acceptable for the investigator to send photocopies of the participant's medical records to the Sponsor in lieu of completion of the AE CRF page.
- There may be instances when copies of medical records for certain cases are requested by the Sponsor. In this case, all participant identifiers, with the exception of the participant number, will be blinded on the copies of the medical records before submission to the Sponsor.
- The investigator will attempt to establish a diagnosis of the event based on signs, symptoms, and/or other clinical information. In such cases, the diagnosis (not the individual signs/symptoms) will be documented as the AE/SAE.

Assessment of severity

- An event is defined as “serious” when it meets at least 1 of the predefined outcomes as described in the definition of an SAE, not when it is rated as severe.
- The investigator will assess the severity for each AE, SAE, and AESI (and other reportable safety event) reported during the study. Severity will be graded according to an adaption of NCI CTCAE version 5.0 as applicable for pediatric assessments. Where necessary, the NCI CTCAE scale has been adapted to conform to AE assessment for infant participants. The severity of solicited injection-site AEs, solicited systemic AEs, elevated temperature, and AESI will be assessed according to the grading criteria (for Grade 1 through Grade 4) provided in [Table 11](#) through [Table 15](#). Additional grading definitions for AEs are provided in the separate study document: Severity Grading for Adverse Events.
- The severity for all other types of AEs that are not in the adapted NCI CTCAE will be determined by the investigator based upon clinical judgment and by using the following severity grading criteria (for Grade 1 through Grade 4):
 - **Grade 1:** Mild; mild symptoms; clinical or diagnostic observations only; intervention not indicated; awareness of symptoms, but easily tolerated.
 - **Grade 2:** Moderate; minimal, local, or noninvasive intervention indicated. Infant is definitely acting like something is wrong.

- **Grade 3:** Severe or medically significant but not immediately life-threatening; intensive intervention indicated; disabling. Infant is extremely irritable or unable to do usual activities.
- **Grade 4:** Life-threatening consequences; urgent intervention indicated.

Any AE that results in death will be assigned a severity grade of Grade 5.

It is important to distinguish between seriousness criteria and severity of an AE. Severity is a measure of intensity whereas seriousness is defined by the criteria in Section 10.3.2. A Grade 3 AE is not necessarily considered an SAE. For example, a Grade 3 headache that persists for several hours may not meet the definition of an SAE and would be considered a nonserious event, whereas a Grade 2 seizure resulting in a hospital admission would be considered an SAE.

Grading Scales for the Assessment of Severity for Solicited Injection-Site AEs, Solicited Systemic AEs, Elevated Temperature, and AESI

Note: Injection-site redness/erythema and injection-site swelling reported from Day 1 through Day 5 postdose will be evaluated by maximum size.

Table 11 Solicited Injection-Site AE Severity Grading Scale

Solicited Injection-Site AE ^a	Severity Grade			
	Grade 1	Grade 2	Grade 3	Grade 4
Pain/Tenderness	Mild pain or tenderness with or without associated symptoms; does not interfere with normal activity	Moderate pain or tenderness. Interferes with normal activity	Severe pain or tenderness; prevents normal activity	Life-threatening consequences; urgent intervention indicated
Erythema/Redness	Size measured as >0 and ≤1	Size measured as >1 and ≤2	Size measured as >2	Necrosis or exfoliative dermatitis OR results in ER visit or hospitalization
Swelling	Size measured as >0 and ≤1	Size measured as >1 and ≤2	Size measured as >2	Necrosis or exfoliative dermatitis OR results in ER visit or hospitalization
AE=adverse event; eDiary=electronic diary; ER=emergency room. ^a Based upon information provided by the legally acceptable representative in the eDiary and verbally during the eDiary review. Erythema/redness and swelling are specific injection-site AEs with size designations of numbers 1 through 8, as indicated on the study-supplied ruler. If the participant has an ER visit or is hospitalized for any injection-site AE, that AE is to be assigned a grade of 4, regardless of the size measured.				

Table 12 Solicited Systemic AE Severity Grading Scale

Solicited Systemic AE ^a	Severity Grade			
	Grade 1	Grade 2	Grade 3	Grade 4
Irritability	Mild; mild symptoms; clinical or diagnostic observations only; intervention not indicated; awareness of symptoms but easily tolerated.	Moderate; minimal local or noninvasive intervention indicated. Infant is definitely acting like something is wrong.	Severe or medically significant but not immediately life-threatening; hospitalization or prolongation of hospitalization indicated; disabling. Infant is extremely irritable or unable to do usual activities.	Life-threatening consequences; urgent intervention indicated.
Drowsiness	Mild; asymptomatic or mild symptoms; clinical or diagnostic observations only; intervention not indicated; awareness of symptoms but easily tolerated.	Moderate; minimal local or noninvasive intervention indicated. Infant is definitely acting like something is wrong.	Severe or medically significant but not immediately life-threatening; hospitalization or prolongation of hospitalization indicated; disabling. Infant is extremely distressed or unable to do usual activities.	Life-threatening consequences; urgent intervention indicated.
Appetite lost	Mild; asymptomatic or mild symptoms; clinical or diagnostic observations only; intervention not indicated; awareness of symptoms but easily tolerated.	Moderate; minimal local or noninvasive intervention indicated. Infant is definitely acting like something is wrong.	Severe or medically significant but not immediately life-threatening; hospitalization or prolongation of hospitalization indicated; disabling. Infant is extremely distressed or unable to do usual activities.	Life-threatening consequences; urgent intervention indicated.
AE=adverse event; eDiary=electronic diary. ^a Based upon information provided by the legally acceptable representative in the eDiary and verbally during the eDiary review.				

Table 13 Elevated Temperature (Rectal) Severity Grading Scale

	Severity Grade			
	Grade 1	Grade 2	Grade 3	Grade 4
Elevated Temperature (°C) ^a	≥38.0 to <39.0	≥39.0 to <40.0	≥40.0	≥40.0
(°F) ^a	≥100.4 to <102.2	≥102.2 to <104.0	≥104.0 for ≤24 hours	≥104.0 for >24 hours
^a Rectal temperature. Correction factors to adjust axillary temperatures for an equivalent rectal temperature are axillary temperature +2 degrees in Fahrenheit OR axillary temperature +1.1 degrees in Celsius.				

Table 14 AESI: Anaphylaxis/Hypersensitivity Severity Grading Scale

AESI Term	Severity Grade			
	Grade 1	Grade 2	Grade 3	Grade 4
Anaphylaxis	Not applicable	Not applicable	Symptomatic bronchospasm, with or without urticaria; parenteral intervention indicated; allergy-related edema/angioedema; hypotension	Life-threatening consequences; urgent intervention indicated
Angioedema	Mild; asymptomatic or mild symptoms; clinical or diagnostic observations only; intervention not indicated; awareness of symptoms, but easily tolerated	Moderate; minimal, local or noninvasive intervention indicated. Infant is definitely acting like something is wrong	Severe or medically significant but not immediately life-threatening; intensive intervention indicated; disabling. Infant is extremely distressed or unable to do usual activities	Life-threatening consequences; urgent intervention indicated
Bronchospasm	Mild symptoms; intervention not indicated	Symptomatic; medical intervention indicated; limiting routine activities such as feeding	Limiting routine activities such as feeding; supplemental oxygen indicated	Life-threatening respiratory or hemodynamic compromise; intubation or urgent intervention indicated
Drug hypersensitivity (drug-related allergic reaction)	Allergic reaction; systemic intervention not indicated	Oral intervention indicated	Bronchospasm; hospitalization indicated for clinical sequelae; intravenous intervention indicated	Life-threatening consequences; urgent intervention indicated
Hypersensitivity	Allergic reaction; systemic intervention not indicated	Oral intervention indicated	Bronchospasm; hospitalization indicated for clinical sequelae; intravenous intervention indicated	Life-threatening consequences; urgent intervention indicated
Dyspnea (difficulty breathing)	Shortness of breath with moderate exertion	Shortness of breath with minimal exertion; limiting routine activities such as feeding	Shortness of breath at rest; limiting routine activities such as feeding	Life-threatening consequences; urgent intervention indicated

AESI Term	Severity Grade			
	Grade 1	Grade 2	Grade 3	Grade 4
Dysphonia	Mild sore throat; raspy voice	Moderate sore throat; analgesics indicated	Severe throat pain; endoscopic intervention indicated	Not applicable
Wheezing	Detectable airway noise with minimal symptoms	Moderate symptoms; medical intervention indicated; limiting routine activities such as feeding	Severe respiratory symptoms limiting routine activities such as feeding; oxygen therapy or hospitalization indicated	Life-threatening consequences; urgent intervention indicated
AESI=adverse event(s) of special interest.				

Table 15 AESI: Rash Severity Grading Scale

AESI Term	Severity Grade			
	Grade 1	Grade 2	Grade 3	Grade 4
Acute generalized exanthematous pustulosis (AGEP)	Not applicable	Not applicable	Severe or medically significant but not immediately life-threatening; hospitalization or prolongation of existing hospitalization indicated; limiting routine activities such as feeding	Life-threatening consequences; urgent intervention indicated
Drug eruption	Lesions covering <10% BSA; topical intervention indicated	Lesions covering 10–30% BSA; oral intervention indicated	Lesions covering >30% BSA; IV intervention indicated	Not applicable
Drug reaction with eosinophilia and systemic symptoms (DRESS)	Not applicable	Not applicable	Severe or medically significant but not immediately life-threatening; hospitalization or prolongation of existing hospitalization indicated; limiting routine activities such as feeding	Life-threatening consequences; urgent intervention indicated
Erythema multiforme	Target lesions covering <10% BSA and not associated with skin tenderness	Target lesions covering 10-30% BSA and associated with skin tenderness	Target lesions covering >30% BSA and associated with oral or genital erosions	Target lesions covering >30% BSA; associated with fluid or electrolyte abnormalities; ICU care or burn unit indicated
Generalized rash of exfoliative nature (including dermatitis exfoliative and exfoliative rash)	Not applicable	Erythema covering >90% BSA without associated symptoms	Erythema covering >90% BSA with associated symptoms (eg, pruritus or tenderness); limiting routine activities such as feeding	Erythema covering >90% BSA with associated fluid or electrolyte abnormalities; ICU care or burn unit indicated

AESI Term	Severity Grade			
	Grade 1	Grade 2	Grade 3	Grade 4
Stevens-Johnson syndrome	Not applicable	Not applicable	Skin sloughing covering <10% BSA with associated signs (eg, erythema, purpura, epidermal detachment, and mucous membrane detachment)	Skin sloughing covering 10–30% BSA with associated signs (eg, erythema, purpura, epidermal detachment and mucous membrane detachment)
Toxic epidermal necrolysis	Not applicable	Not applicable	Not applicable	Skin sloughing covering ≥30% BSA with associated symptoms (eg, erythema, purpura, or epidermal detachment)
Urticaria (hives or welts)	Urticarial lesions covering <10% BSA; topical intervention indicated	Urticarial lesions covering 10-30% BSA; oral intervention indicated	Urticarial lesions covering >30% BSA; IV intervention indicated	Not applicable
AESI=adverse event(s) of special interest; BSA=body surface area; ICU=intensive care unit; IV=intravenous.				

Assessment of causality

- Did the Sponsor's product cause the AE?
- The determination of the likelihood that the Sponsor's product caused the AE will be provided by an investigator who is a qualified physician. The investigator's signed/dated initials on the source document or worksheet that supports the causality noted on the AE form, ensures that a medically qualified assessment of causality was done. This initialled document must be retained for the required regulatory time frame. The criteria below are intended as reference guidelines to assist the investigator in assessing the likelihood of a relationship between the test product and the AE based upon the available information.
- **The following components are to be used to assess the relationship between the Sponsor's product and the AE;** the greater the correlation with the components and their respective elements (in number and/or intensity), the more likely the Sponsor's product caused the AE:
 - **Exposure:** Is there evidence that the participant was actually exposed to the Sponsor's product such as: reliable history, acceptable compliance assessment (diary, etc.), seroconversion?
 - **Time Course:** Did the AE follow in a reasonable temporal sequence from administration of the Sponsor's product? Is the time of onset of the AE compatible with a vaccine-induced effect?
 - **Likely Cause:** Is the AE not reasonably explained by another etiology such as underlying disease, other drug(s)/vaccine(s), or other host or environmental factors?
 - **Rechallenge:** Was the participant re-exposed to the Sponsor's product in the study?
 - If yes, did the AE recur or worsen?
 - If yes, this is a positive rechallenge.
 - If no, this is a negative rechallenge.

(Note: This criterion is not applicable if: (1) the initial AE resulted in death or permanent disability, or (2) the study is a single-dose intervention study; or (3) Sponsor's product(s) is/are used only 1 time.)

NOTE: IF A RECHALLENGE IS PLANNED FOR AN AE THAT WAS SERIOUS AND MAY HAVE BEEN CAUSED BY THE SPONSOR'S PRODUCT, OR IF RE-EXPOSURE TO THE SPONSOR'S PRODUCT POSES ADDITIONAL POTENTIAL SIGNIFICANT RISK TO THE PARTICIPANT THEN THE RECHALLENGE MUST BE APPROVED IN ADVANCE BY THE SPONSOR CLINICAL DIRECTOR, AND IF REQUIRED, THE IRB/IEC.

- **Consistency with study intervention profile:** Is the clinical/pathological presentation of the AE consistent with previous knowledge regarding the Sponsor's product or drug class pharmacology or toxicology?
- The assessment of relationship will be reported on the CRFs/worksheets by an investigator who is a qualified physician according to their best clinical judgment, including consideration of the above elements.
- Use the following scale of criteria as guidance (not all criteria must be present to be indicative of a Sponsor's product relationship).
 - Yes, there is a reasonable possibility of Sponsor's product relationship:
 - There is evidence of exposure to the Sponsor's product. The temporal sequence of the AE onset relative to the administration of the Sponsor's product is reasonable. The AE is more likely explained by the Sponsor's product than by another cause.
 - No, there is not a reasonable possibility of Sponsor's product relationship:
 - Participant did not receive the Sponsor's product OR temporal sequence of the AE onset relative to administration of the Sponsor's product is not reasonable OR the AE is more likely explained by another cause than the Sponsor's product. (Also entered for a participant with overdose without an associated AE.)
- The investigator must review and provide an assessment of causality for each AE/SAE and document this in the medical notes.
- There may be situations in which an SAE has occurred and the investigator has minimal information to include in the initial report to the Sponsor. However, it is very important that the investigator always make an assessment of causality for every event before the initial transmission of the SAE data to the Sponsor.
- The investigator may change their opinion of causality in light of follow-up information and send an SAE follow-up report with the updated causality assessment.
- The causality assessment is 1 of the criteria used when determining regulatory reporting requirements.

Follow-up of AE and SAE

- The investigator is obligated to perform or arrange for the conduct of supplemental measurements and/or evaluations as medically indicated or as requested by Sponsor to elucidate the nature and/or causality of the AE or SAE as fully as possible. This may include additional laboratory tests or investigations, histopathological examinations, or consultation with other health care professionals.
- New or updated information will be recorded in the CRF.

- The investigator will submit any updated SAE data to the Sponsor within 24 hours of receipt of the information.

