8.3.3 Body Temperature Measurement

Rectal or axillary temperature will be taken by study staff predose and postdose at the 30-minute postdose safety observation period at the RSV Season 1 Day 1 visit and at the subsequent required scheduled and unscheduled visits, as indicated in the SoA (Section 1.3).

Rectal is the preferred method of obtaining participant's temperature, where allowed by local practice. Axillary (underarm) is an acceptable method. Use of oral, temporal, or tympanic thermometers to collect temperature for this study is **not** permitted.

Additionally, the participant's legally acceptable representative will be asked to record a temperature reading and method of measurement (rectal or axillary) in the eDiary for 5 days after each dose. Temperature readings should be taken at approximately the same time each day with the thermometer provided by the study.

If an elevated temperature is detected using the axillary method ($\geq 100.0^{\circ}\text{F}$ [$\geq 37.8^{\circ}\text{C}$]), the temperature should be confirmed by rectal measurement, where allowed by local practice. Only the confirmatory rectal measurement should be recorded. If the rectal measurement cannot be performed, the original axillary measurement should be recorded.

Fever is defined as any rectal temperature $\geq 102.2^{\circ}\text{F}$ ($\geq 39.0^{\circ}\text{C}$) or axillary temperature $\geq 101.7^{\circ}\text{F}$ ($\geq 38.7^{\circ}\text{C}$). All fevers must be reported Day 1 through 14 days post Dose 2 and for 14 days after each subsequent dose in RSV Season 1 and for 42 days postdose in RSV Season 2 unless the fever is a symptom of another reported AE. In addition, all fevers must be reported for 42 days postdose for participants who receive an additional post-surgery dose of MK-1654 in either RSV Season 1 or 2. If a temperature is recorded in the eDiary that

meets this definition of fever, the site should call the legally acceptable representative to inquire about respiratory symptoms or any other symptoms. If no other symptoms are present the fever should be reported as an AE.

8.3.4 30-Minute Postdose Safety Observation

Participants will be monitored at the study site during a 30-minute postdose observation period for any signs/symptoms of:

- An immediate anaphylaxis/hypersensitivity AE (see Section 8.4.8.1);
- An immediate rash AE (see Section 8.4.8.2);
- Injection-site AEs (including redness/erythema, swelling, and tenderness/pain); and
- Any other AEs.

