9.4.2 Safety Endpoints

Safety and tolerability will be assessed by clinical review of all relevant parameters including AEs, physical examinations, and vital signs.

The primary safety endpoints for RSV Season 1 are:

- Number of participants with solicited injection-site AEs (redness/erythema, swelling, and pain/tenderness) from Days 1 through 5 after each dose.

- Number of participants with fever (defined as maximum rectal temperature $\geq 102.2^{\circ}\text{F}$ [$\geq 39.0^{\circ}\text{C}$] or axillary temperature $\geq 101.7^{\circ}\text{F}$ [$\geq 38.7^{\circ}\text{C}$]) from Days 1 through 5 after each dose.
- Number of participants with solicited systemic AEs (irritability, drowsiness, and appetite lost) from Days 1 through 5 after each dose.
- Number of participants with anaphylaxis/hypersensitivity AESI from Days 1 through 28 after Dose 1 and Days 1 through 14 after Dose 2.
- Number of participants with rash AESI from Days 1 through 28 after Dose 1 and Days 1 through 14 after Dose 2.
- Number of participants with any nonserious AEs from Days 1 through 28 after Dose 1 and 14 days after each subsequent dose.
- Number of participants with SAEs through the duration of participation in RSV Season 1.

The secondary safety endpoints for RSV Season 2 are:

- Number of participants with solicited injection-site AEs (redness/erythema, swelling, and pain/tenderness) from Days 1 through 5 postdose.
- Number of participants with fever (defined as maximum rectal temperature $\geq 102.2^{\circ}\text{F}$ [$\geq 39.0^{\circ}\text{C}$] or axillary temperature $\geq 101.7^{\circ}\text{F}$ [$\geq 38.7^{\circ}\text{C}$]) from Days 1 through 5 postdose.
- Number of participants with solicited systemic AEs (irritability, drowsiness and appetite lost) from Days 1 through 5 postdose.
- Number of participants with anaphylaxis/hypersensitivity AESI from Days 1 through 42 postdose.
- Number of participants with rash AESI from Days 1 through 42 postdose.
- Number of participants with any nonserious AEs from Days 1 through 42 postdose.
- Number of participants with SAEs from Days 1 through 180 postdose.

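### For infants with only an axillary temperature on record, the fever cut-offs imply a 0.3 °C axillary-to-rectal offset while the Table 13 severity scale uses 1.1 °C, so the same reading can be Grade 2 and not a fever.

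*Combined protocol and SAP*

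**What the plan says.** **Fever definition.** Section 8.3.3 begins its definition "Fever is defined as any rectal temperature" and sets the limits at rectal 39.0 °C (102.2 °F) or axillary 38.7 °C (101.7 °F). The synopsis and Sections 3 and 8.3.5 use the same pair. Section 9.4.2 carries it into the primary Season 1 endpoint, "Number of participants with fever (defined as maximum rectal temperature" at or above 39.0 °C, or axillary at or above 38.7 °C, on Days 1 to 5 after each dose. The Season 2 secondary endpoint uses the same limits.

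**Severity.** In Section 10.3.5, the severity of "elevated temperature, and AESI will be assessed according to the grading criteria (for Grade 1 through Grade 4" in Tables 11 to 15. Table 13 works on the rectal scale: Grade 1 is "≥38.0 to <39.0" °C, Grade 2 runs from 39.0 to below 40.0 °C, and Grades 3 and 4 start at 40.0 °C, separated by duration. Its footnote says that the factors for "an equivalent rectal temperature are axillary temperature +2 degrees in Fahrenheit OR axillary temperature +1.1 degrees in Celsius".

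**Measurement route.** Section 8.3.3 prefers rectal readings but adds: "Axillary (underarm) is an acceptable method". An axillary reading of 37.8 °C or more should be confirmed rectally where local practice permits, and then only the rectal value is recorded. If no rectal reading can be taken, the axillary value stays on record.

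**The concern.** The fever definition and Table 13 both rely on a relation between axillary and rectal temperature, and the two relations differ. Table 13's Grade 2 floor is exactly the rectal fever limit, so a reader would expect Grade 2 or above and fever to coincide. They do for rectal readings. They do not for an axillary value left on record.

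At stake is how fever is described. Fever is a primary safety endpoint and, under Section 9.6.2, a Tier 2 comparison with a 95% CI. By the protocol's own conversion, an infant with only an axillary value must be hotter to count as a fever case than one measured rectally, so the reported proportion depends partly on local measuring practice. The Season 2 fever proportion is described without a between-group comparison, so there is no concurrent control against which such an effect could cancel. Severity tables are affected as well, because axillary fevers move almost at once into Grade 3 or higher.

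**Working it through.** **Inputs**

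- Fever limits: rectal 39.0 °C / 102.2 °F; axillary 38.7 °C / 101.7 °F (Sections 3, 8.3.3, 8.3.5, 9.4.2).
- Table 13 factor: +1.1 °C / +2 °F.
- Table 13 grades, rectal scale: Grade 2 from 39.0 to <40.0 °C (102.2 to <104.0 °F); Grades 3 and 4 from 40.0 °C (104.0 °F).
- Trigger for rectal confirmation: axillary 37.8 °C (Section 8.3.3).

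**Step 1: are the stated figures sound in their own units?** With °C = (°F − 32) × 5/9, 102.2 °F = 39.0 °C and 101.7 °F = 38.72 °C. A difference of 2 °F is 2 × 5/9 = 1.11 °C. Each rule is consistent between the two scales, so neither is a unit slip.

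**Step 2: offset implied by the fever limits.** 39.0 − 38.7 = 0.3 °C, and 102.2 − 101.7 = 0.5 °F. The illness criterion in Section 5.2 (rectal 38.1 °C, axillary 37.8 °C) gives the same: 38.1 − 37.8 = 0.3 °C.

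**Step 3: apply the Table 13 factor to the fever limits.**

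- Axillary fever limit on the rectal scale: 38.7 + 1.1 = 39.8 °C (101.7 + 2 = 103.7 °F).
- Axillary reading equivalent to the rectal fever limit: 39.0 − 1.1 = 37.9 °C (102.2 − 2 = 100.2 °F).
- Gap from the axillary limit in use: 38.7 − 37.9 = 0.8 °C (101.7 − 100.2 = 1.5 °F).

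**Step 4: classify axillary readings at 0.1 °C resolution.**

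| Axillary reading (°C) | Table 13 equivalent (°C) | Grade | Fever? |
|---|---|---|---|
| 37.8 | 38.9 | 1 | No |
| 37.9 to 38.6 | 39.0 to 39.7 | 2 | No |
| 38.7 to 38.8 | 39.8 to 39.9 | 2 | Yes |
| 38.9 and above | 40.0 and above | 3 or higher | Yes |

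Of the ten axillary readings that convert to Grade 2 (37.9 to 38.8 °C), eight are not fever. In Fahrenheit the discordant band is 100.2 to 101.6 °F, converting to 102.2 to 103.6 °F.

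**Step 5: who can fall in the band?** All of it lies above the 37.8 °C trigger. Where rectal confirmation is done, the rectal value decides both fever and grade, and the rules agree. Only infants whose axillary value stays on record are affected. The documents do not give their share, so no count follows.

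**The case against.** The strongest answer is the confirmation rule. Every reading in the discordant band should prompt a rectal measurement, and the rectal value then replaces the axillary one. A reader might infer from the two offsets that fevers are missed whenever an axillary thermometer is used; Section 8.3.3 does not support that. The rule narrows the conflict but does not remove it, because confirmation depends on local practice and the protocol keeps the axillary value when confirmation cannot be done.

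The endpoint is also explicit. It names two limits and no conversion factor, so every reading can be classified as fever or not without ambiguity. That stands. So does the point that a graded temperature without fever is built into Table 13, since Grade 1 starts at 38.0 °C rectal. The anomaly is specific to Grade 2, whose floor is the rectal fever limit.

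It can further be argued that a sub-threshold axillary reading may never be graded, because Section 8.3.3 ties fever reporting to the fever definition. Section 10.3.5 nevertheless lists elevated temperature among the graded events, so the text leaves this open. The grading of axillary readings that do meet the fever definition does not depend on it.

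Finally, a reader might infer a biased treatment comparison. The documents do not support that. Allocation is randomised 1:1, Part 1 is double-blind up to the Day 60 visit (Section 6.3.3), and the primary safety comparison covers the first two doses (Section 9.6.2). Section 8.3.2 asks for the same method throughout for each participant. Local practice should therefore act alike on both arms in that comparison.

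**Conclusion.** The inconsistency holds, in a limited form. For infants with only an axillary value on record, the fever definition and Table 13 differ by 1.1 − 0.3 = 0.8 °C. The consequences are a band of readings (37.9 to 38.6 °C) that is Grade 2 without being fever, and axillary fevers that are Grade 2 over only two tenths of a degree-step, 38.7 and 38.8 °C.

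The effect falls on absolute fever rates, including the uncontrolled Season 2 description, and on severity tables. The number of infants cannot be computed. The conclusion assumes that the Table 13 factor is applied to axillary readings as its footnote states, and that rectal confirmation is not possible for some participants, which Section 8.3.3 provides for.

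This is an internal inconsistency rather than an arithmetic error: each figure is right in its own units. The 0.3 °C offset recurs in the protocol's other rectal and axillary pairs and 1.1 °C appears only in Table 13, but that does not establish which relation was intended.

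**What to change.** 1. Reconcile the Table 13 correction factor with the paired fever limits in the synopsis and Sections 3, 8.3.3, 8.3.5 and 9.4.2, so that one axillary-to-rectal relation applies throughout. Which relation is for the sponsor to decide.
2. In the same pass, check the 38.1/37.8 °C pairs in Sections 5.2, 5.2.1, 8.1.8.1 and 8.13.1 and the 37.8 °C confirmation trigger in Section 8.3.3.
3. State in Section 9.6.2 whether the summary of maximum temperature by Brighton Collaboration cut-offs uses raw or converted axillary values.
4. Optionally, tabulate fever by measurement method. The eDiary already records the method, so no new data are needed.

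The cost is a change of wording in either the footnote or the definitions, one added sentence in Section 9.6.2, and one extra table if item 4 is adopted. Reported fever counts or severity grades may shift, depending on which text is changed.
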